### **5.2.2 Gray Oral Reading Test**

The Gray Oral Reading Test (GORT) will be used to measure reading comprehension. The GORT is one of the most widely used measures of oral reading fluency and comprehension in the United States. Participants will be asked to read a set of passages and recall specific details from the stories. Responses to the test require literal as well as inferential comprehension, the latter of which involves executive function. Two stories will be given each day, one day from Form A and one day from Form B. Raw scores will be calculated for total accuracy, and compared within participants. Total testing time will be approximately 5 minutes after each clinical tDCS session.

### **5.2.3 Woodcock Johnson Understanding Directions**

The Woodcock Johnson Understanding Directions is a measure of listening comprehension. The task requires the participant to listen to a series of complex instructions and then follow the directions by pointing to various objects in a colored picture. Directions require sequential and logical reasoning, components of executive function. Four complex instructions will be administered each day, from alternate test forms, and raw scores will be calculated and compared within participants. Total testing time will be approximately 5 minutes after each clinical tDCS session.

### **5.2.4 Remote Assessment Procedures**

We have recently completed a pilot study to evaluate the accuracy of remote cognitive assessment, using web and phone based procedures. We will employ these procedures prior to

and following the initiation of phase II of the trial. Specifically, the following tests will be administered:

**Televideo-based assessment:**

Neurocognitive testing will be conducted via video conferencing with the iPad. At a scheduled time, an examiner will contact the participant. The following clinical measures will be administered:

- Digit Span Test
- Verbal Fluency Test
- Oral Trail Making Test
- CCSS Neurocognitive Questionnaire

## **6 CRITERIA FOR REMOVAL FROM PROTOCOL**

### **6.1 Off Study Criteria:**

**6.1.1** All protocol interventions are complete

**6.1.2** Request of the Participant/Legally Authorized Representative

**6.1.3** Death

**6.1.4** Lost to follow-up

**6.1.5** Discretion of the Study PI, such as the following:

- The researcher decides that continuing in the study would be harmful
- A treatment is needed that is not allowed on this study
- The participant misses so many appointments that the data cannot be used in the study
- New information is learned that a better treatment is available, or that the study is not in the participant's best interest

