In phase II, the feasibility and efficacy of long-term (5 week) self-administration of the tDCS intervention will be evaluated in concurrence with self-administered cognitive stimulation. In this phase the research participants will be taught to use the mobile tDCS device and will be provided with one to take home. The device will be programmed by the investigators in advance to control the intensity and duration of the stimulation. The research participants will use the device twice per week as directed. Before each session, the participant will use an institutionally provided iPad for video conferencing with the study center to obtain a unique access code to start the tDCS device and ensure proper device placement. Each stimulation session for each participant will have a unique access code. An AE evaluation will be conducted by a trained study team member every week. Research participants will complete remote neurocognitive testing via the iPad before and after phase II.

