#### **4.2.3 Cognitive Training:**

Survivors who complete phase I and continue to phase II will begin the 5 week cognitive stimulation program. Participants will use the supplied iPad to complete online cognitive stimulation training within one hour of every at-home tDCS session. The cognitive training program was developed by Lumosity (see Appendix for description of Lumosity program) and involves training of attention, processing speed, working memory, and executive function skill using cognitive tasks. Participants will be asked to engage in training for 20 minutes a day, two days per week. Five cognitive tasks will be presented during each training session. Survivors will complete 5-weeks of stimulation and training. The Lumosity program records the day and time of training and performance on the training activities for each participant, and these records are available to study staff via internet. Adherence to training and

change in performance following stimulation sessions will be examined.

At the end of the 5-week intervention, participants will mail back the iPad and tDCS device in a postage-paid and addressed FedEx box provided to them at their study visit.

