### **Analysis:**

Objective 1.1.1: The feasibility of the 5-week tDCS intervention will be evaluated using Simon's two stage Minimax design with stopping rules described above.

Objective 1.2.1: The improvement in scores on symbol digit coding, Stroop test, shifting attention test, digit span and verbal fluency from baseline to 5-week follow up will be done using matched pair one sample t-tests. In addition, the improvement in EF measures over the 5 week period will also be evaluated using longitudinal methods and implemented using PROC MIXED or PROC GEE in SAS 9.3.

Objective 1.2.2: The improvement in the scores on the NIH Toolbox Card Sort, Flanker and Working Memory tasks between tDCS and sham, will be done using matched pair one sample t-test.

It will be important to monitor for AEs in both phases of the study as well. Thus, in an "ad hoc" manner using one sided 95% confidence bounds we will monitor for all grade 3 or higher adverse events (All types of AE's included)

which are related to study interventions. Among the 45 patients enrolled in the study, if at any time point at least 5 patients ( $\geq 5$ ) have grade 3 or higher toxicity, the 95% lower confidence limit would be 0.059 suggesting that the true AE rate could be higher than 5% which would be unacceptable, the feasibility of the 5 week intervention would be questionable and a consideration will be given to stop or amend the trial.

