## APPENDIX I: SCHEDULE OF EVALUATIONS

Event	Screening	Phase 1		Mobile Intervention Period					
		Day 1	Day 2	Pre Intervention	Week 1	Week 2	Week 3	Week 4	Week 5
Informed Consent	X								
Cognitive Assessment	X								
TDCS Clinical Intervention		X	X						
TDCS Mobile Intervention					X	X	X	X	
Cognitive Stimulation					X	X	X	X	
NIH Toolbox Cognitive Battery		X	X						
Remote Cognitive Assessment				X					X

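### Section 6.1 does not separate stopping the intervention from leaving the study, so the Week 5 assessment of early stoppers is not secured and the paired test for objective 1.2.1 may rest on a selected subset

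*Combined protocol and SAP*

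**What the plan says.** Section 6.1 (Off Study Criteria) is the only list of exit rules in the protocol. It contains:

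- 6.1.1: "All protocol interventions are complete".
- 6.1.2: "Request of the Participant/Legally Authorized Representative", with no distinction between declining further sessions and declining further assessment.
- 6.1.3 and 6.1.4: death and loss to follow-up.
- 6.1.5: investigator discretion. The examples include "The researcher decides that continuing in the study would be harmful", need for a treatment the study does not permit, and "The participant misses so many appointments that the data cannot be used in the study". No number of missed appointments is given.

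On outcome assessment, Section 4.1 says: "Research participants will complete remote neurocognitive testing via the iPad before and after phase II". Appendix I marks "Remote Cognitive Assessment" at Pre Intervention and at Week 5, and has no early-termination column. Section 4.2.3 says: "At the end of the 5-week intervention, participants will mail back the iPad and tDCS device". It does not say when someone who stops early returns the equipment.

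On analysis, Section 9 (Objective 1.2.1) says that improvement "from baseline to 5-week follow up will be done using matched pair one sample t-tests", and adds a longitudinal analysis in PROC MIXED or GEE. It gives no analysis population and no rule for missing scores. The power statement in Section 9 uses 37 participants, with no allowance for missing Week 5 scores.

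**The concern.** Harm, a disallowed treatment and poor attendance are reasons that would usually stop an intervention. Here they are written as reasons to leave the study. If someone who stops home sessions is also taken off study, the Week 5 score is not collected, and that person drops out of a paired test. Those left would be the participants who tolerated the device and kept to the schedule. Persistence over five weeks may be related to executive function, which is both the impairment being treated and the outcome being measured.

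Objective 1.2.1 is to estimate efficacy, and Section 9 describes the pilot as the basis for a later randomised trial. An estimate from a subset selected in this way could mislead the planning of that trial.

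**Working it through.** **Inputs.** All are from Section 9 unless noted: n = 37; improvement of 0.65 in standardised units (taken as SD of the paired change); alpha 0.05 (sidedness not stated; two-sided assumed); feasibility boundary of 24 of 37 completing at least 5 of 10 sessions. The number of participants who would lack a Week 5 score is not given, so the values of 30 and 24 below are assumptions.

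**Step 1: reproduce the plan's power.** Two-sided normal approximation: power = Φ(0.65 × √37 − 1.960) = Φ(3.954 − 1.960) = Φ(1.994) = 0.977. This matches the stated 97.7%. The two-sided noncentral t gives 97.0%.

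**Step 2: power if some Week 5 scores are missing.** The same formulas with fewer pairs:

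| Pairs with both scores | Normal | Noncentral t |
|---|---|---|
| 37 | 97.7% | 97.0% |
| 30 | 94.5% | 93.1% |
| 24 | 89.0% | 86.2% |

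For 24 pairs: Φ(0.65 × √24 − 1.960) = Φ(3.184 − 1.960) = Φ(1.224) = 0.890. The loss of power is moderate.

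**Step 3: selection in the estimate (illustration).** Let a fraction f be assessed with mean gain 0.65 SD, and let the rest have mean gain g. The gain over all 37 is 0.65f + g(1 − f). With f = 24/37 = 0.649:

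- g = 0: 0.65 × 0.649 = 0.42 SD
- g = 0.325 (half of 0.65): 0.422 + 0.325 × 0.351 = 0.54 SD
- g = 0.65: 0.65 SD, so no bias

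The paired test would report 0.65 SD in each case. The values of g are assumptions, and 0.65 is the effect in the power statement, not a predicted gain.

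**Step 4: can the longitudinal analysis repair this?** The remote assessment is scheduled at only two times. PROC MIXED can include a participant with only a pre-Phase II score, but for that person it relies on missingness at random given the observed data. If the missing outcome depends on why the person stopped, the model does not recover it.

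**The case against.** A reader might infer that early stoppers have no Week 5 assessment and that the test is a completers-only analysis. The documents do not support that reading:

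- Stopping sessions is not itself an off-study trigger, and 6.1.5 is discretionary.
- The attendance example concerns data that have become unusable. Someone who does 3 of 10 sessions need not meet it.
- Section 4.1 and Appendix I schedule the assessment without any condition on sessions completed. The plan is silent on early stoppers; it does not exclude them.
- A paired test uses everyone with both scores, however few sessions they did.

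A reader might also infer that completers lose their assessment because the iPad goes back at the end of the intervention. An assessment in Week 5 followed by return fits both Section 4.2.3 and Appendix I. For completers, 6.1.1 needs only a wording repair.

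Nor are the 13 of 37 at the feasibility boundary known to lack a Week 5 score. They are participants with fewer than 5 sessions, some of whom might still be assessed. Section 9 also counts as failures those who finish Phase I but refuse Phase II because of the tDCS procedure, and they never start home sessions.

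Finally, 1.2.1 is a secondary objective, and Phase II has no control group, so its pre-post change cannot isolate efficacy even with full follow-up.

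All of this stands, and it limits the point to what the plan leaves open. It does not supply what is missing: an off-intervention status, a stated follow-up for those who stop, an analysis population, or a missing-data rule.

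**Conclusion.** The point holds as a gap with a plausible consequence. Whether an early stopper is assessed at Week 5 is left to discretion under exit criteria that are partly about tolerance and attendance, and the paired test then analyses whoever has both scores. The stronger claim, that the estimate is completers-only and overstates the gain, is not established.

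The size of any bias is unknown. The range of 0.42 to 0.54 SD against 0.65 SD holds only if 24 of 37 are assessed and the others gain between nothing and half as much; equal gains give no bias. The stated 97.7% power needs all 37 to have both scores. Possible selection in the estimate matters more than the loss of power. The primary feasibility endpoint counts sessions and does not depend on Week 5 scores. For a secondary objective in a pilot, this is a change that should be made because it is cheap and affects which data are collected.

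**What to change.** 1. Split Section 6 into off-intervention and off-study criteria.
2. Amend 6.1.1 so that it is met only when both the interventions and the post-Phase II remote assessment are complete.
3. State that anyone with a pre-Phase II assessment who stops sessions early is asked to do the scheduled Week 5 remote assessment, which involves no stimulation. The exceptions are withdrawal of consent, or the investigator's judgement that the assessment itself should not be done.
4. In Section 4.2.3, have the iPad returned after that assessment.
5. In Section 9, analyse 1.2.1 on all participants with a pre-Phase II score and at least one home session, regardless of sessions completed. Use those completing at least 5 sessions as a secondary set. Report how many lack a Week 5 score and why, and state how missing scores are handled.

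The remote call yields scores only for the measures it contains. Of the five measures named in Section 9 for 1.2.1, only digit span and verbal fluency are in the televideo battery of Section 5.2.4. The two lists need to be reconciled for all participants, completers included.

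The cost is edits to Sections 6.1, 4.2.3 and 9, one remote call per early stopper, later iPad return for those participants, and possibly a smaller reported effect. The feasibility endpoint and its stopping rules do not change.

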## **7 SAFETY AND ADVERSE EVENT REPORTING REQUIREMENTS**

### **7.1 Reporting Adverse Experiences and Deaths to St. Jude IRB**

**Only “unanticipated problems involving risks to participants or others” referred to hereafter as “unanticipated problems” are required to be reported to the St. Jude IRB promptly, but in no event later than 10 working days after the investigator first learns of the unanticipated problem.**

**Regardless of whether the event is internal or external (for example, an IND safety report by the sponsor pursuant to 21 CFR 312.32), only adverse events that constitute unanticipated problems are reportable to the St. Jude IRB. As further described in the definition of unanticipated problem, this includes any event that in the PI's opinion was:**

- Unexpected (in terms of nature, severity, or frequency) given (1) the research procedures that are described in the protocol-related documents, such as the IRB-approved research protocol and informed consent document, as well as other relevant information available about the research; (2) the observed rate of occurrence (compared to a credible baseline for comparison); and (3) the characteristics of the subject population being studied; and
- Related or possibly related to participation in the research; and
- Serious; or if not serious suggests that the research places subjects or others at a greater risk of harm (including physical, psychological, economic, or social harm) than was previously known or recognized.

Unrelated, expected deaths do not require reporting to the IRB. Though death is “serious”, the event must meet the other two requirements of “related or possibly related” and “unexpected/unanticipated” to be considered reportable.

Deaths meeting reporting requirements are to be reported immediately to the St. Jude IRB, but in no event later than 48 hours after the investigator first learns of the death.

**The following definitions apply with respect to reporting adverse experiences:**

**Serious Adverse Event: Any adverse event temporally associated with the subject's participation in research that meets any of the following criteria:**

- results in death;
- is life-threatening (places the subject at immediate risk of death from the event as it occurred);
- requires inpatient hospitalization or prolongation of existing hospitalization;
- results in a persistent or significant disability/incapacity;

- results in a congenital anomaly/birth defect; or
- any other adverse event that, based upon appropriate medical judgment, may jeopardize the subject's health and may require medical or surgical intervention to prevent one of the other outcomes listed in this definition (examples of such events include: any substantial disruption of the ability to conduct normal life functions, allergic bronchospasm requiring intensive treatment in the emergency room or at home, blood dyscrasias or convulsions that do not result in inpatient hospitalization, or the development of drug dependency or drug abuse), a congenital anomaly/birth defect, secondary or concurrent cancer, medication overdose, or is any medical event which requires treatment to prevent any of the medical outcomes previously listed.

**Unexpected Adverse Event:**

- Any adverse event for which the specificity or severity is not consistent with the protocol-related documents, including the applicable investigator brochure, IRB approved consent form, Investigational New Drug (IND) or Investigational Device Exemption (IDE) application, or other relevant sources of information, such as product labeling and package inserts; or if it does appear in such documents, an event in which the specificity, severity or duration is not consistent with the risk information included therein; or
- The observed rate of occurrence is a clinically significant increase in the expected rate (based on a credible baseline rate for comparison); or
- The occurrence is not consistent with the expected natural progression of any underlying disease, disorder, or condition of the subject(s) experiencing the adverse event and the subject's predisposing risk factor profile for the adverse event.

**Internal Events: Events experienced by a research participant enrolled at a site under the jurisdiction of St. Jude IRB for either multicenter or single-center research projects.**

**External Events:** Events experienced by participants enrolled at a site external to the jurisdiction of the St. Jude Institutional Review Board (IRB) or in a study for which St. Jude is not the coordinating center or the IRB of record.

**Unanticipated Problem Involving Risks to Subjects or Others:** An unanticipated problem involving risks to subjects or others is an event which was not expected to occur and which increases the degree of risk posed to research participants. Such events, in general, meet all of the following criteria:

- unexpected;
- related or possibly related to participation in the research; and
- suggests that the research places subjects or others at a greater risk of harm (including physical, psychological, economic, or social harm) than was previously known or recognized. An unanticipated problem involving risk to subjects or others may exist even when actual harm does not occur to any participant.

**Consistent with FDA and OHRP guidance on reporting unanticipated problems and adverse events to IRBs, the St. Jude IRB does not require the submission of external events, for example IND safety reports, nor is a summary of such events/reports required; however, if an event giving rise to an IND safety or other external event report constitutes an “unanticipated problem involving risks to subjects or others” it must be reported in accordance with this policy. In general, to be reportable external events need to have implications for the conduct of the study (for example, requiring a significant and usually safety-related change in the protocol and/or informed consent form).**

**Although some adverse events will qualify as unanticipated problems involving risks to subjects or others, some will not; and there may be other unanticipated problems that go beyond the definitions of serious and/or unexpected adverse events. Examples of unanticipated problems involving risks to subjects or others include:**

- Improperly staging a participant’s tumor resulting in the participant being assigned to an incorrect arm of the research study;

- The theft of a research computer containing confidential subject information (breach of confidentiality); and
- The contamination of a study drug. Unanticipated problems generally will warrant consideration of substantive changes in the research protocol or informed consent process/document or other corrective actions in order to protect the safety, welfare, or rights of subjects or others.

All anticipated Grade III or IV adverse events will be reported to the IRB in the continuing review report and/or summary. The study teams will monitor accrual and toxicities every six months.

## **7.2 Recording Adverse Events and Serious Adverse Events**

All serious adverse events will be recorded in the source, database and/or case report form. Adverse events unrelated to the trial will not be recorded unless they are grade III or above (CTCAEv4). Adverse events that are related to the trial will be captured in the source document, database and/or case report form. Adverse events related to the trial will be collected until the time the study completes.

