tDCS and found that 56% of studies reported mild AEs and no studies reported more than mild AE's. The most common AE's reported were itching, tingling, mild headache, and discomfort, however, none of the AE's differed in frequency between the placebo (sham application) and active treatment groups. Levels of less than 2 mA of current over 5-20 minutes for 1-10 days has been used in various studies without significant adverse events. In addition, clinical studies have demonstrated efficacy of tDCS intervention in reducing neurocognitive impairments among patients suffering from strokes, depression, psychosis, and Alzheimer's disease. However, the usefulness of tDCS has not been evaluated in long-term adult survivors of childhood cancer exhibiting neurocognitive impairments. Since these adults have likely experienced neurocognitive impairment for many years, we believe the application of tDCS will enhance their ability to benefit from cognitive training.

We propose to conduct a pilot study to assess the feasibility and potential efficacy of a 5-week tDCS intervention paired with cognitive training to improve executive function in long-term adult survivors of childhood ALL. Stimulation and training will be conducted at home twice per week for five weeks. However, prior to initiating the home trial, we propose to conduct a trial in the clinic in order to evaluate the short-term effect of tDCS on measures of executive function. This clinic-based trial will also provide participants with on-sight experience with tDCS under direct observation prior to beginning the home-based intervention under remote observation.

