#### **4.2.2 Transcranial Direct Current Stimulation – Mobile System:**

The mobile transcranial direct current stimulation system is manufactured by Soterix Medical and consists of a battery pack, control unit and a self-positioning headband with sponges. Participants will be given the device after completing the clinical portion of the study and trained in correct usage. Participants will complete two stimulation sessions per week for 5 weeks. The sessions will provide 1 mA DC for 15 minutes in the same manner as the clinical system. Participants will be supplied iPads for the cognitive stimulation training, and the iPad will be used to monitor correct tDCS usage. The tDCS unit requires a unique code for each stimulation session. Study staff will use video conferencing to confirm correct electrode placement, then provide the code to initiate treatment. Each session will be monitored for compliance and to assess any adverse events.

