#### **4.3 Adverse Event Monitoring:**

Reports of adverse events will be monitored. Adverse events will be surveyed at the beginning of each video conference, with symptoms reports for the prior stimulation session. Adverse event information will be collected by participant reporting and direct questioning using the patient report of incidence of side effects (PRISE), frequency and intensity of side effect rating (FISER), and global rating of side effects burden (GRSEB). The PRISE form assesses the presence of side effects for a variety of biological systems. For each of the nine organ/function systems (gastrointestinal, nervous system, heart, eyes/ears, skin, genital/urinary, sleep, sexual functioning, and other), the participant indicates the presence of a side effect, and if present, the tolerability of the side effect (tolerable or distressing). The FISER and GRSEB assess three domains of side effect impact: frequency, intensity, and burden. Each domain is rated on a 7-point Likert scale (i.e. Frequency, ranging from no side effects to present all the time; Intensity, ranging from no side effects to intolerable; and Burden, ranging from no impairment to unable to function due to side effects). Reliability and validity have been reported.

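### Section 7.2 leaves non-serious grade 1–2 events judged unrelated out of the record although Section 4.3 already asks about them, so low-grade home side-effect rates depend on unspecified causality calls

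*Combined protocol and SAP*

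**What the plan says.** Section 7.2 sets three recording rules. For serious events: "All serious adverse events will be recorded in the source, database and/or case report form". For related events, with no grade limit: "Adverse events that are related to the trial will be captured in the source document, database and/or case report form". For the rest: "Adverse events unrelated to the trial will not be recorded unless they are grade III or above", with grading by CTCAE version 4.

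Section 4.3 describes how events are elicited: "Adverse events will be surveyed at the beginning of each video conference, with symptoms reports for the prior stimulation session". The instruments are PRISE, FISER and GRSEB, given by participant report and direct questioning. "The PRISE form assesses the presence of side effects for a variety of biological systems"; it covers nine organ or function systems and, where a side effect is present, asks how well it is tolerated. FISER and GRSEB rate frequency, intensity and burden on 7-point scales.

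The frequency of assessment in the home phase is described in two ways. Section 4.2.2 agrees with Section 4.3: "Each session will be monitored for compliance and to assess any adverse events". Section 4.1 says: "An AE evaluation will be conducted by a trained study team member every week".

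Section 2.2 reports from a published review that none of the adverse events "differed in frequency between the placebo (sham application) and active treatment groups".

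**The concern.** The plan asks about symptoms in a structured way and then applies an attribution filter before low-grade events enter the record. In Phase II every participant receives active stimulation, so no concurrent control rate exists against which to judge a complaint. The protocol states no criteria for relatedness, names no one to decide it and describes no second review. The plan's own background says the usual symptoms are mild and as frequent on sham as on active treatment. If that is so, a single case gives little basis for deciding cause, and rates across participants are the more useful evidence.

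What is at stake is the low-grade tolerability profile of the home device, which a later randomized trial would draw on. Section 7.1 also relies on rates: it treats an event as unexpected if its observed rate is clinically significantly above the expected one, allows non-serious events to count as reportable problems, and has the team review toxicities every six months. Those judgements are weaker if individual calls have already removed events from the record.

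**Working it through.** The plan gives no low-grade side-effect rate, so there is no figure to reproduce. The check sets the sections side by side and then shows how the filter acts on a rate.

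**1. What reaches the record under Section 7.2**

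| Event | Judged related | Judged unrelated |
|---|---|---|
| Serious | Recorded | Recorded |
| Non-serious, grade III or above | Recorded | Recorded |
| Non-serious, grade 1–2 | Recorded | Not recorded |

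Only one cell is affected.

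**2. What the forms supply under Section 4.3.** They give presence, tolerability, frequency, intensity and burden. They are not described as asking about cause or CTCAE grade. Two judgements, grade and relatedness, therefore stand between a completed form and the adverse event record, and the protocol specifies no procedure for the second.

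**3. What happens to the forms.** Section 8.1 describes data handling for baseline and follow-up assessments, neurocognitive tests, NIH Toolbox, the mobile units and Lumosity. It does not mention the side-effect forms. No section says that they are entered or kept, and none says that they are thrown away.

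**4. How many forms.** Two sessions a week for 5 weeks is 2 × 5 = 10 sessions per participant. On the per-session reading that is about 10 sets of forms each, or 37 × 10 = 370 for 37 Phase II participants. On the weekly reading it is 5 each, or 37 × 5 = 185.

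**5. Effect on a rate.** Let T be the proportion of participants with a non-serious grade 1–2 event at home from any cause, and m the share of those events judged unrelated. With at most one such event per participant, the recorded rate is R = T × (1 − m). The documents give neither T nor m, so all values below are assumptions.

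| Assumed T | m = 0% | m = 10% | m = 25% | m = 50% |
|---|---|---|---|---|
| 20% | 20% | 18% | 15% | 10% |
| 50% | 50% | 45% | 37.5% | 25% |

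The relative shortfall equals m whatever T is. It is zero if no event is judged unrelated.

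**6. Direction of error for device-caused events.** Split the events into C caused by the device and B background. If a share s of the caused events and a share f of the background events are judged related, the recorded count is sC + fB. This is below C when fB < (1 − s)C and above C when the inequality is reversed. The direction is therefore fixed for the all-cause rate but not for the caused rate.

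**7. Planned analyses that use the affected cell.** There are none. In Section 9 the primary outcome is session completion, the secondary analyses are of cognitive scores, and the safety rule counts related events of grade 3 or higher. Unrelated events of grade III or above are recorded, so the attribution behind that rule can be reviewed.

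**The case against.** The strongest case against is that Section 7.2 governs adverse event recording only, while Section 4.3 separately collects the same information on structured forms. A reader might infer that low-grade unrelated events are discarded and can never be rechecked. The documents do not support that: they are silent on retention. If the forms are kept, rates without attribution can be computed later. This stands, and the point is limited accordingly. What remains is that the plan does not guarantee it.

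A reader might also infer that reported tolerability is biased low. That holds for the all-cause rate only. With no sham in Phase II, an all-cause count includes ordinary background complaints and may overstate what the device does. The finding that sham and active frequencies do not differ points the same way. This stands too: the all-cause table does not supply the missing comparator, and the two tables are more informative together than either alone.

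A further argument is that the forms ask about side effects of the prior session, so they are not an all-cause inventory. It has some force, since participants may leave out complaints that they do not link to stimulation. But a participant's report is not the relatedness judgement that Section 7.2 applies, and that judgement remains undefined.

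Finally, some oversight exists: monthly team meetings, six-monthly toxicity review, and semi-annual monitoring of adverse event recording in up to 15% of participants (Sections 7.1 and 8.2). That is partial, and the adverse event record alone would not show a monitor an event that was never entered. Filtering low-grade events by attribution may also be a deliberate choice in a pilot described as low risk. That supports a low priority, but it does not settle who judges relatedness or what happens to the forms.

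**Conclusion.** The point holds as a minor, inexpensive improvement to the recording rule. A low-grade home side-effect rate taken from the recorded adverse events would understate the all-cause rate by the share of events judged unrelated. That share is unknown and could be near zero. This rests on reading Section 7.2 as written, and on the side-effect forms not being entered by some other route. The calls behind such a rate can be rechecked only if the forms are kept.

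A reader might go on to infer that the trial's safety conclusions are compromised. They are not: Section 9 plans no grade 1–2 rate, and both the grade 3 or higher rule and the recording of serious events are untouched. Nor do the documents establish that the forms are used in Phase I, because Section 4.3 places the survey at video conferences. A tDCS-versus-sham comparison of side effects therefore cannot be assumed to be available.

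**What to change.** 1. Amend Section 7.2 so that all PRISE, FISER and GRSEB responses collected under Section 4.3 are entered in the database whatever their judged cause.
2. Hold relatedness as a separate field, and state who decides it and by what criteria.
3. Tabulate Phase II events twice, regardless of relatedness and as related, with a note that the all-cause counts include background complaints.
4. Reconcile Section 4.1 (weekly) with Sections 4.2.2 and 4.3 (each session or conference) on how often adverse events are assessed.
5. State whether the forms are used in Phase I. Tabulate by tDCS versus sham there only if they are.

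The cost is data entry for forms that Section 4.3 already has participants complete, about 5 or 10 sets per home participant depending on how item 4 is settled. No study procedure is added. The reported side-effect rates will look less favourable. The change should be made before data collection, since events left out of the record may not be recoverable.
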